## **10.11 Interim Analysis**

No formal interim analysis is planned for this study. The database will be locked for the analysis of the Main Period when all data up to and including Week 16 have been collected and cleaned, and the BDRM has taken place. All endpoints in the Main Period will be analyzed after unblinding, which will take place after all subjects have completed the assessments at Week 20 due to operational reasons. A database snapshot will be performed during the Extension

---

Period. A second database lock will be performed after all data of the Extension Period have been collected and cleaned, and the corresponding analyses of endpoints will be performed.

An independent, unblinded Data Monitoring Committee (DMC) will receive data for safety reviews at prespecified time points in order to detect and report early evidence of unanticipated harm to subjects (see Section 13.3). To maintain the blind, the data for the safety reviews will be delivered by an unblinded CRO biostatistics team located at a different geographical site to the blinded CRO biostatistics personnel involved in the study.

## **11 ETHICAL, LEGAL, AND ADMINISTRATIVE ASPECTS**

### **11.1 Good Clinical Practice Statement**

All persons participating in the conduct of the study (sponsor, investigators, etc.) commit themselves to observe the Declaration of Helsinki (version Fortaleza 2013) as well as all pertinent national laws and the ICH guidelines for GCP issued in June 1996 and CPMP/ICH/135/95 from September 1997.

### **11.2 Submission to the Ethics Committee and Responsible Regulatory Authority**

The protocol and other associated documents will be submitted to the applicable Ethics Committee for approval. The study documents will be submitted to the applicable regulatory authority.

The study can only start after obtaining a positive evaluation by the applicable Ethics Committee and approval from the applicable regulatory authority. The written approval of the applicable Ethics Committee and the responsible regulatory authority must be filed in the trial master file. Additionally, each study site must receive a copy of these documents to be filed in the investigator site file.

### **11.3 Subject Information and Informed Consent**

The investigator must explain to each study subject the nature of the study, the purposes, the procedures involved, the expected duration, the potential risks and benefits involved, and any discomfort it may entail to each study subject. They must be informed that participation in the study is voluntary, that they may withdraw their consent to participate at any time, and that withdrawal of consent will not affect the subsequent medical treatment of the study subject or the relationship to the treating physician.

The informed consent must be given by means of standard written statements, written in non-technical language. The subjects should read the informed consent form and consider their decision before signing and dating the document. A copy of the signed document must be given to the subject. No subject can be involved in the study if he/she is related to the investigator, any member of the team at the study site, or the sponsor.

The informed consent of the subject must also refer specifically to the assessment and processing of data on the subject's health. The subject is to be informed explicitly on the purpose and extent of the assessment and the use of their personal data, especially the health-related data.

Subjects may also be asked to provide informed consent to have photographs taken of their disease response during the study.

An additional informed consent form respecting the principles described above will be used for subjects participating in the PK substudy.

---

## 11.4 Protocol Amendments

Changes made to the protocol that was appraised positively by the Ethics Committee and approved by the responsible federal authority must be positively reappraised and approved by the Ethics Committee and the responsible federal authority if the changes:

- Are such that they may affect the subjects' safety
- Are fundamental to the therapeutic procedures
- Result in further data collection that necessitates changes to the subject information and/or informed consent form
- Affect the interpretation of the scientific documents upon which the study is based or the significance of the results of the study
- Significantly affect the leadership or conduct of the study
- Concern the quality or the innocuousness of the investigational drug

Protocol amendments need the authorization of the sponsor, the coordinating investigator, and the responsible biostatistician, if applicable. All protocol amendments will be:

- Submitted to the Ethics Committee and, where applicable, to the responsible federal authority
- Provided in written form to the responsible parties
- Filed in the trial master file

## 12 DOCUMENTATION

### 12.1 Electronic Case Report Forms

All data beside ePRO required by this clinical study protocol will be collected in an eCRF and entered into a database validated by the CRO for eCRFs.

The sponsor or its designee will supply the study site with eCRFs. The sponsor or its designee will make arrangements to train appropriate study site personnel in the use of the eCRF.

These eCRFs are used to transmit information collected on the performance of this study to the sponsor and regulatory authorities. eCRFs must be completed in English.

Data entered in the eCRF will be stored in a centralized database on a remote server. Data will be entered by study site personnel who can access the system through a personal user identification and password assigned by the system administrator.

Data will be entered directly into the eCRF via a single data entry process. In the eCRF, subjects will be identified by their subject numbers. The eCRF is to be dated and signed by the investigator or a qualified person who has been delegated by the investigator to do so on his/her behalf, as documented on a signature delegation log filed in the investigator site file.

After completion of the entry process, computer logic checks will be run to identify items, such as inconsistent dates, missing data and questionable values. Queries may be issued by sponsor personnel (or designees) and will be answered by the site.

Corrections to the eCRF database are recorded in an audit trail that captures a complete record of all information. The new information, identification of the person making the correction, the date the correction was made, and the reason for change are captured in a new record.

---

The principal investigator must review the eCRFs for completeness and accuracy and must sign and date the appropriate eCRFs as indicated. Furthermore, the principal investigator must retain full responsibility for the accuracy and authenticity of all data entered into the eCRFs.

The eCRFs will be reviewed for completeness and acceptability at the study site during periodic visits by the clinical monitor. The sponsor and/or its designee will be permitted to review the subject's medical and hospital records pertinent to the study to ensure accuracy of the eCRFs. The completed eCRFs are the sole property of the sponsor and should not be made available in any form to third parties, except for authorized representatives of appropriate governmental health or regulatory authorities, without written permission of the sponsor.

Further information on handling of the eCRF data (e.g., data entry, clarification, and validation) will be defined in the data management plan.

## **12.2 Archiving**

Because the study is being conducted to obtain marketing authorization, the requirements of ICH Guideline E6 section 5.5.11 and 5.5.12 shall be taken into account.

The investigator is responsible for archiving the investigator site file, the subject's records, and the source data according to applicable regulatory requirements. These documents have to be archived for at least 10 years, but should be retained for longer if required by regulatory stipulations or by agreement with the sponsor.

If the investigator can no longer maintain the archive of study records (e.g., due to retirement or relocation), the sponsor must be informed in writing about any change in responsibility for record retention, including the name of the new responsible party, contact information, and location of the study records. Records must not be destroyed without prior written consent from the sponsor.

## **13 SUPERVISION OF THE CLINICAL STUDY**

### **13.1 Access to Source Data**

According to ICH guidelines for GCP and the applicable laws, the investigator must permit all authorized third parties access to the study site and the medical records of the study subjects (source data). These include the clinical monitors, auditors, and other authorized employees of the sponsor as well as members of the local or federal authorities. All these persons are bound to strict confidentiality.

### **13.2 Monitoring**

Monitoring of the study sites will be performed by a CRO designated by the sponsor and will be based on the CRO's monitoring standard operating procedures (SOPs) as well as the study specific monitoring manual.

The clinical monitor, as a representative of the sponsor, has the obligation to follow the study closely. The monitor will visit the study site at periodic intervals in addition to maintaining necessary telephone calls and written contact as appropriate. The monitor will maintain a working knowledge of the study through observation, review of study records and source documentation, and discussion of the conduct of the study with the investigator and study site personnel. Source data verification of the eligibility criteria as described in the monitoring manual will be performed for all subjects.

---

The monitor will report via the project manager of the sponsor designated CRO to the sponsor who carefully monitors all aspects of the study for compliance with applicable government regulations, with respect to current ICH guidelines for GCP and current SOPs.

As part of the responsibilities assumed by participating in the study, the investigator agrees to maintain adequate case histories for the subjects treated under this protocol. The investigator agrees to maintain accurate source documentation and eCRFs as part of the case histories.

Study records are comprised of source documents, eCRFs, and all other administrative documents (e.g., correspondence, clinical study materials, supply shipping manifests, or monitoring logs). An investigator site file will be provided with instructions for the maintenance of study records.

### **13.3 Independent Data Monitoring Committee**

An independent, unblinded DMC will be established to allow regular monitoring of the study data in order to detect and report early evidence of unanticipated harm to subjects. The Independent DMC will meet after a defined number of subjects have completed the Main Period. The number of subjects is defined in the Independent DMC Charter. Further ad hoc reviews may be arranged and conducted if deemed necessary.

The reviews will focus on safety data from the double-blind treatment phases, including but not limited to TEAEs, drug exposure, laboratory test results, and vital sign measurements. Further details of the data and outputs to be provided to the DMC will be described in the DMC SAP. A DMC charter will provide further details on the DMC membership, the responsibilities of the DMC, the purpose and timing of the reviews, and the procedures for ensuring confidentiality and proper communication. The charter will also outline the required content of the written report to be provided by the DMC after each safety review, including their recommendations for the future conduct of the study.

To maintain the blind, the data for the safety reviews will be delivered by an unblinded CRO biostatistics team located at a different geographical site to the blinded CRO biostatistics personnel involved in the study. Apart from the actual decisions, these data will not be shared with anyone outside of the attendees of the safety review meeting until after the double-blind treatment phase database lock. A detailed blinding and communication plan will be agreed upon by InflaRx and the responsible CRO to clarify the distribution of the unblinded information and the level of blinding (eg, summary data, individual data).

### **13.4 Audits**

In order to guarantee that the conduct of the study is in accordance with ICH guidelines for GCP and the national laws, audits may be performed at the study sites to be carried out by an independent auditor. In addition, for-cause audits may be scheduled.

The investigator agrees to give the auditor access to all relevant documents for review.

### **13.5 Inspections**

According to the corresponding ICH guidelines for GCP, inspections of the study sites may be performed by the local or federal authorities at any time during or after completion of the study.

The investigator agrees to give the inspectors access to all relevant documents for review.

---

## **14 DATA PROTECTION AND CONFIDENTIALITY**

Within this study, personal data from the study subjects and data regarding the treatment and the course of subject's welfare will be collected.

The data will be stored and processed in anonymized form (i.e., without reference to the subject's name) with the aid of a unique subject identification number.

Data will be managed by a sponsor designated CRO (data entry, data cleaning, and data exports). The safety concept ensures among other things that data access is limited to authorized persons, that measures are taken to prevent loss of data, and that the applicable laws pertaining to data protection are observed. The data are protected from third party access and only members of the study team are permitted access. These members are bound to strict confidentiality.

Personal data will be stored in an anonymous manner after reaching finishing completion status of all concomitant scientific projects for at least 15 years, if no other or new regulatory requirements come into effect warranting different time periods for archiving.

### **14.1 Declaration Regarding Data Protection**

During data entry, processing, and analysis by a sponsor designated CRO, all requirements of the data protection act will be taken into account. Access to data is strictly limited to authorized persons. Data are protected against unauthorized access.

### **14.2 Declaration Regarding the Anonymized Transfer of Personal Data**

The sponsor certifies herewith that the transfer of anonymized personal data will take place according to the applicable local laws. Moreover, the sponsor certifies that study subjects who do not permit the transfer of data will not be admitted to the study.

## **15 ADMINISTRATIVE AGREEMENTS**

### **15.1 Adherence to the Protocol/Protocol Violations**

The clinical study described here will be conducted and analyzed in accordance with local laws and ICH guidelines for GCP.

After a subject has been enrolled, it is the investigator's responsibility to avoid protocol violations in order to obtain unbiased data for the analysis of the study.

All protocol violations will be documented and discussed with the responsible biostatistician before closing the database and carrying out the statistical analyses.

### **15.2 Financing and Insurance**

The study is financed by the sponsor.

The subjects are covered by an applicable insurance policy for participation in a clinical study. A copy of the insurance policy and the insurance conditions will be filed in the investigator site file.

---

## 15.3 Notification of the Local Authorities

The sponsor, their contractors, and all investigators and their deputies are responsible for notifying the local regulatory authority of their participation in the study prior to enrollment of the first subject in the study. Responsibility for notification to the local authorities has been delegated to a sponsor designated CRO.

This extends also to amendments, discontinuation of study arms or of the entire study, and the regular conclusion of the study.

## 15.4 Publication Policy and Registration

### 15.4.1 Publication Policy

The rights and obligations of investigators and the sponsor concerning any formal presentation or publication of data collected as a direct or indirect result of this study will be addressed specifically in the Clinical Study Agreement for the study.

The first publication must be based upon all data obtained from all analyses, as stipulated in the study protocol.

The sponsor must receive a copy of any intended communications in advance of the proposed submission date. This is to allow the sponsor time to review the communication for accuracy (thus avoiding potential discrepancies with submissions to regulatory authorities), to verify that confidential and/or proprietary information is not inadvertently divulged, to provide any relevant supplementary information, and to allow establishment of co-authorship (as appropriate). The authorship of communications arising from pooled data will include investigators from study sites that contributed data as well as relevant personnel from the sponsor. Ownership of all data will remain with the sponsor.

Furthermore, the publication policy will follow the recommendations of Good Scientific Practice of the Deutsche Forschungsgemeinschaft ([www.dfg.de](http://www.dfg.de)) and will meet the criteria of the International Committee of Medical Journal Editors (<http://www.icmje.org>).

### 15.4.2 Registration

The sponsor will provide the relevant study protocol information in a public database (e.g., ClinicalTrials.gov, <https://clinicaltrials.gov/>) before or at commencement of the study. The sponsor may also provide study information for inclusion in national registries according to local regulatory requirements.

If a potential subject contacts the sponsor regarding participation in the study, the investigator agrees that the sponsor may forward the study site and contact details to the subject. Based on the inclusion and exclusion criteria for the study, the investigator will assess the suitability of the subject for enrollment into the study.

Results of this study will be disclosed according to the relevant regulatory requirements. All publications in peer-reviewed medical journals resulting from this study will be listed in the original study protocol registration record (e.g., on ClinicalTrials.gov).

---

## 17 APPENDIX

### 17.1 Hurley Stages

Evaluation of disease severity after Hurley [13].

Grade I	Abscess formation, single or multiple, without sinus tracts or cicatrization
Grade II	Recurrent abscesses, with sinus tract formation and cicatrization; single or multiple, widely separated lesions One or more widely separated recurrent abscesses with tract formation and cicatrization
Grade III	Diffuse or near-diffuse involvement, or multiple interconnected tracts and abscesses across entire area Multiple interconnected tracts and abscesses across the entire area, with diffuse or near-diffuse involvement

---

## 17.2 Hidradenitis Suppurativa-Physician's Global Assessment

The HS-PGA disease severity scale includes the following definitions [20]:

Severity	Score	Definition
Clear	0	0 abscesses, 0 draining fistulas, 0 inflammatory nodules, and 0 non-inflammatory nodules
Minimal	1	0 abscesses, 0 draining fistulas, 0 inflammatory nodules, and presence of non-inflammatory nodules
Mild	2	0 abscesses, 0 draining fistulas, and 1 to 4 inflammatory nodules or 1 abscess or draining fistula (sum of abscesses and draining fistulas is 1) and 0 inflammatory nodules
Moderate	3	0 abscesses, 0 draining fistulas, and $\geq 5$ inflammatory nodules or 1 abscess or draining fistula and $\geq 1$ inflammatory nodule or 2 to 5 abscesses or draining fistulas (sum of abscesses and draining fistulas is 2 to 5) and $< 10$ inflammatory nodules
Severe	4	2 to 5 abscesses or draining fistulas and $\geq 10$ inflammatory nodules
Very severe	5	$> 5$ abscesses or draining fistulas (sum of abscesses and draining fistulas $> 5$ )

---

## 17.3 Modified Sartorius Score

Algorithm for calculating the mSS [23].

Calculate several regional scores for each valid local anatomical region. The total mSS is obtained by adding together the single regional mSS.

The following algorithm is used for calculating the regional score based on lesion counts in 12 anatomic regions:

- Left axilla
- Right axilla
- Left sub/inframammary area
- Right sub/inframammary area
- Intermammary area
- Left buttock
- Right buttock
- Left inguino-crural fold
- Right inguino-crural fold
- Perianal
- Perineal area
- Other (to be specified)

For each anatomic region, calculate the regional score as follows:

1. Count 3 points for each regional mSS to account for the identified local region involved
2. For each regional mSS, add points per number and score of lesions (abscesses, nodules, fistulas, scars) within the respective identified local anatomical region:
  - + 2 \* Number of inflammatory nodules
  - + 2 \* Number of non-inflammatory nodules
  - + 4 \* Number of abscesses
  - + 4 \* Number of draining fistulas
  - + 4 \* Number of non-draining fistulas
  - + 1 \* Number of hypertrophic scars
3. For each regional score, add the following points for the longest distance between 2 relevant lesions (i.e., nodules and fistulas) in each identified local anatomical region, or size of lesion:
  - 0 points, if no active lesions
  - 2 points, if the longest distance between 2 relevant lesions or size (if only 1 lesion is present, the diameter of the corresponding lesion is measured) is < 50 mm
  - 4 points, if the longest distance between 2 relevant lesions or size is ≥ 50 mm and < 100 mm
  - 6 points, if the longest distance between 2 relevant lesions or size is > 100 mm

---

4. Are lesions clearly separated by normal skin?

- Yes: 0 points
- No: 6 points

If this question was left unanswered and is thus missing for 1 identified local anatomical region, the score will be recorded as missing for the corresponding subject and time point.

The total mSS is the sum of the 12 regional scores.

---

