### 8.2.2 Methods of Assessment

#### 8.2.2.1 Hidradenitis Suppurativa Clinical Parameters

To evaluate the severity of illness, the following HS clinical parameters will be assessed and documented at Screening, at Week 0 (Day 1), and at prespecified times during the study, as outlined in the [Schedules of Assessments](#) through Week 44 or an early discontinuation visit and the 3-month Post-Treatment Follow-Up visit, if the subject discontinues before Week 44:

- Affected area (i.e., left and right axilla, left and right sub/inframammary area, intermammary area, left and right buttock, left and right inguino-crural fold, perianal, perineal area, other [to be specified]), as described in guidance provided to the investigator

NOTE: lesions in each affected area will be counted. The identification of lesions will be performed according to standard definitions of elementary cutaneous lesions.

- 
- Number and type of lesions (i.e., abscesses, inflammatory nodules, non-inflammatory nodules, non-draining fistulas, draining fistulas, hypertrophic scars, other lesions [folliculitis, pustules])
  - Longest distance between 2 relevant lesions (mm)
  - Are lesions clearly separated by normal skin? (yes/no)

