### **8.2.2.4 Modified Sartorius Score (mSS)**

The mSS is a summation of HS lesions based on a number of factors including anatomical region, number and type of lesions, and distance between relevant lesions measured as HS

---

clinical parameters [23]. The mSS has a minimum value of 0 and no upper limit and is calculated using data recorded for HS clinical parameters in the eCRF (Section 8.2.2.1) according to the algorithm in Appendix 17.3.

The mSS and the corresponding change from Day 1 will be assessed at each of the prespecified times when the HS clinical parameters are scheduled to be assessed during the study, as outlined in [Schedules of Assessments](#).

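### Step 3 of the modified Sartorius Score leaves abscesses out of the lesion distance, so abscess-only regions fit no band and a nodule that becomes an abscess may leave the regional score undefined, flat or lower

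*Combined protocol and SAP*

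**What the plan says.** Appendix 17.3 scores each of 12 regions in four steps and adds the results.

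- **Step 1:** 3 points for an involved region.
- **Step 2:** 2 points per nodule (inflammatory or not), 4 per abscess, 4 per fistula (draining or not), 1 per hypertrophic scar.
- **Step 3:** the instruction is "For each regional score, add the following points for the longest distance between 2 relevant lesions (i.e., nodules and fistulas"), or for lesion size. The bands are 2 points below 50 mm, 4 points from 50 to below 100 mm, and 6 points above 100 mm. The zero band is "0 points, if no active lesions". For a lone lesion the text says that "if only 1 lesion is present, the diameter of the corresponding lesion is measured".
- **Step 4:** 0 or 6 points, according to whether normal skin separates the lesions. The algorithm's only missing-value rule belongs to this step.

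Section 8.2.2.4 says that the mSS "is calculated using data recorded for HS clinical parameters in the eCRF (Section 8.2.2.1"). The one length listed in Section 8.2.2.1 is "Longest distance between 2 relevant lesions (mm"). That section names abscesses as a lesion type of their own and lists no lesion size.

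Section 10.4.1 makes the mSS (values, absolute and relative change from Day 1, by time point) a secondary efficacy endpoint. Section 10.10 replaces missing values only for HiSCR at Week 16.

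**The concern.** Steps 2 and 3 work on different lesion sets. Nodules and abscesses are counted separately everywhere else in the protocol, so the word nodules in step 3 cannot be read to cover abscesses. The zero band then brings in a third set, active lesions, which is not defined.

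The mismatch shows when a lesion changes type. An inflammatory nodule that becomes an abscess gains 2 points in step 2 but leaves the set on which step 3 depends, and the loss in step 3 can cancel or outweigh the gain. The protocol's other scales treat this change as a worsening. If a nodule and an abscess replaced two inflammatory nodules as a subject's only lesions, HS-PGA would move from mild (2) to moderate (3). A rise in abscesses over Day 1 also rules out HiSCR.

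At stake is whether a secondary endpoint is defined, and points the right way, in regions containing abscesses. An undefined regional value leaves the 12-region total undefined, with no rule for what to do.

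**Working it through.** The plan gives no worked mSS figure to reproduce, so the check applies the Appendix 17.3 weights to simple regions. Step 4 is held at 0 (lesions separated by normal skin). A single lesion is assumed to be under 50 mm across unless stated otherwise. Exactly 100 mm falls in no band, which is a separate gap, so the examples avoid it.

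Regional score = 3 + step 2 points + step 3 points.

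**Two inflammatory nodules, one becomes an abscess.** Before: 3 + 2×2 = 7 plus step 3. After: 3 + 2 + 4 = 9 plus step 3. Three readings of step 3 are possible after the change:

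- A, literal: two lesions are present, so the single-lesion clause does not apply; only one is relevant, so there is no distance. Step 3 has no value.
- B: the single-lesion clause is applied to the one remaining relevant lesion, giving 2 points.
- C: the abscess counts towards the distance.

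| Distance | Before | After, A | After, B | After, C |
|---|---|---|---|---|
| 40 mm | 7+2 = 9 | undefined | 9+2 = 11 (+2) | 9+2 = 11 (+2) |
| 75 mm | 7+4 = 11 | undefined | 9+2 = 11 (0) | 9+4 = 13 (+2) |
| 120 mm | 7+6 = 13 | undefined | 9+2 = 11 (−2) | 9+6 = 15 (+2) |

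**When the score falls.** The change is +2 + (new step 3 − old step 3). It is negative only if step 3 drops from 6 to 2, that is, from above 100 mm to below 50 mm. If the remaining nodule is 60 mm wide, reading B gives 9 + 4 = 13, so 13 stays 13. With three nodules in a line and an outer one becoming an abscess, the change is again −2, 0 or +2. It is −2 only when the outer span exceeds 100 mm and the remaining span is under 50 mm.

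**Two abscesses, no nodule or fistula.** Steps 1 and 2 give 3 + 2×4 = 11. There is no relevant pair, more than one lesion is present, and abscesses are hardly inactive, so no step 3 line applies. With abscesses counted, the score is 13, 15 or 17 at 40, 75 or 120 mm.

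**Two non-inflammatory nodules 120 mm apart.** Both are relevant lesions. Whether they are active is not stated: 3 + 4 + 0 = 7 if not, 3 + 4 + 6 = 13 if so.

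**Single lesions.** A nodule scores 3 + 2 + 2 = 7 and a draining fistula 3 + 4 + 2 = 9. An abscess scores 3 + 4 + 2 = 9 if the clause covers any lesion, and has no step 3 value if it covers relevant lesions only.

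**The case against.** A reader might infer more than the documents support, in four ways.

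- **That single-lesion regions cannot be scored.** Appendix 17.3 has an explicit rule for them, and any lone nodule or fistula under 50 mm gets 2 points.
- **That the diameter is not collected.** Appendix 17.3 says that it is measured, the eCRF is not in the document, and a site could enter it in the millimetre field. What can be shown is that Section 8.2.2.1 does not list it. Scoring a lone inflammatory nodule 0 in step 3 for want of a diameter would use a rule that appears nowhere.
- **That worsening from nodule to abscess generally lowers the score.** The fall needs reading B and a drop from the top band to the bottom one. Otherwise the score is flat, rises or is undefined.
- **That the subjects who change most are the ones affected.** The documents give no frequency for abscess-only regions or for spans above 100 mm.

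Two further arguments have weight. Section 10.1 leaves exact endpoint definitions to a separate SAP, whose text is not in the document reviewed and which could define relevant and active lesions before unblinding. The score is also attributed to a cited publication that cannot be consulted here, so the omission of abscesses may follow the instrument.

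These arguments narrow the point but do not remove it. The distance is taken by the investigator at each visit. If sites measure only between nodules and fistulas, a later SAP cannot recover a distance that includes an abscess, or a diameter that was never entered. Even if the lesion set follows the source, abscess-only regions still need a step 3 value.

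**Conclusion.** The step 3 wording is defective as written. Regions with two or more abscesses and no nodule or fistula have no step 3 value. For a nodule that becomes an abscess, step 3 is undefined on the literal words. On the most natural workaround the regional change is +2, 0 or −2 points, where counting abscesses gives +2 in every band. For a region left with one nodule and one abscess, the two workable readings differ by up to 4 points (11 against 15 at 120 mm). These figures assume a remaining nodule under 50 mm and step 4 unchanged. The effect on cohort means cannot be estimated from the documents.

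The consequence is limited. The mSS is one of several secondary endpoints, and Section 10.5.1 commits only to descriptive summaries for it, with models left to the SAP as deemed necessary. The primary HiSCR analysis and the sample size do not use it. This should be corrected, but it does not threaten the trial's main conclusion.

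**What to change.** In Appendix 17.3 step 3, use one lesion set throughout: inflammatory and non-inflammatory nodules, abscesses, and draining and non-draining fistulas. Measure the longest distance over that set, apply the single-lesion clause to it, and give 0 points only when none of these lesions is present. In Section 8.2.2.1 and on the eCRF label for the distance item, add: or diameter (mm) if only one lesion is present. It would also help to extend the missing-value rule from step 4 to step 3.

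With this change, the nodule-to-abscess example rises by 2 at 40, 75 and 120 mm, two abscesses score 13, 15 or 17, and a single abscess under 50 mm scores 9.

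The cost is wording in two sections and one field label, with no extra visits. The downside is slightly reduced comparability with earlier uses of the cited score. If the sponsor prefers to keep abscesses out of the distance for that reason, the appendix should say so and state what step 3 gives for abscess-only and nodule-plus-abscess regions.
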